5 LIMITATIONS

While claims data are extremely valuable for the efficient and effective examination of health care outcomes, treatment patterns, health care resource utilization, and costs, claims data are collected for the purpose of payment and not research. Therefore, there are certain limitations associated with the

use of claims data. First, presence of a claim for a filled prescription does not indicate that the medication was consumed or that it was taken as prescribed. Second, medications filled over-the-counter or provided as samples by the physician will not be observed in the claims data. Third, presence of a diagnosis code on a medical claim is not positive presence of disease, as the diagnosis code may be incorrectly coded or included as rule-out criteria rather than actual disease. Finally, certain information is not readily available in claims data that could inform study outcomes, especially certain clinical and disease-specific parameters; therefore, spirometry results are not included. To mitigate these limitations, multiple claims for diagnosis and treatment are required for sample identification and patients are asked about their COPD diagnosis and current treatment in the survey. Limitations of survey data may include sampling error, coverage error (including lower response rates for commercially versus publicly sponsored studies), and measurement error. Because the population will be selected from Medicare Advantage enrollees, the results may not be generalizable to patients with Medicare Fee for Service coverage, uninsured populations, or to younger patients with COPD. To limit the proportion of patients who may have dual insurance coverage, patients are required to be age 65 or older at the beginning of the sample identification period; however, it is possible some patients may have dual coverage, which may underestimate their costs and utilization.

6 STUDY CONDUCT MANAGEMENT & ETHICS

6.1 Ethics Committee/IRB Approval

6.1.1 Health Plan Approval

Use of a health plan recruitment strategy requires that the study concept be approved by the large U.S. health plan affiliated with Optum since patients will be identified in the plan's health care claims data. Optum will submit the study design to the health plan's Research Review Board (RRB) for approval. Approval by the RRB is not guaranteed. Since the study involves Medicare Advantage patients, the study concept must also be approved through the compliance process of the large U.S. health plan affiliated with Optum. Optum will submit the study concept to the health plan's Medicare Advantage compliance review team for approval. Approval by the health plan's Medicare Advantage compliance review team is not guaranteed.

6.1.2 Health Plan Medicare Advantage Plan Approval

Use of a health plan recruitment strategy with Medicare Advantage plan patients requires all patient data collection and communication materials (e.g., survey instrument, informed consent statement, study invitation letters, reminder postcard, missing materials letter, and thank you letter) to be approved by the health plan's compliance review team to ensure appropriate communications with Medicare Advantage plan patients. After GSK has approved the study protocol and survey instrument, Optum will submit all patient communication materials to the health plan's MA compliance review team for approval. Approval by the health plan's MA review team is not guaranteed.

6.1.3 Institutional Review Board Approval

Optum will work with a central IRB to obtain appropriate approvals for the study, including patient recruiting and consenting procedures. Regulatory, independent ethics, and any other review and approval will be obtained and maintained in the study file. The subject informed consent statement will be approved by a central IRB prior to the start of the study.

Optum will prepare and submit the appropriate documents to a central IRB for review and approval. The submission package will contain documents specified by the central IRB, which will include:

- Complete or sections of the study protocol

- Data collection instruments
- Subject consent materials
- Documentation of forms of communication with the study subject

Optum will communicate directly with the central IRB to address any questions and provide any additional information requested in connection with the central IRB's review. Optum will not begin subject recruitment until IRB approval of all components of the study is obtained.

6.2 Informed Consent

As part of the IRB submission, Optum will request a waiver of documentation of informed consent. If approved, the study packet will contain IRB-approved informed consent statement, which does not require signature. The consent form will ask patients to return the study survey if they elect to participate in the study. Consent is implied when patients return study materials, and signed consent will not be obtained. Patients may withdraw consent at any time.

Consent documentation informs participants that they may withdraw consent by contacting the Optum study project manager, including their contact information. After aggregate results have been published, subject data cannot be removed from published results. In the rare event that a subject withdraws consent after agreeing to participate (i.e., by returning a completed survey), it is usually proximal to the survey data collection period and prior to results dissemination. In that case, the subject will be removed from all analyses and their survey destroyed.

6.3 Data Protection

Optum will adhere to ethical and legal requirements for protection of participants' privacy and confidentiality, Optum's established practices for collection and validation of data, and preparation of a reliable database for statistical analysis.

Physical Security

Optum has established strict physical and environmental controls to protect information assets and information technology systems from unauthorized physical access, safeguard against reasonable environmental hazards, and preserve the safety of personnel.

Network Security

Optum employees complete a two-tiered security awareness-training program. The first tier requires all employees to understand the basic principles of security. The second tier involves security awareness training and additional technical training for our information technology staff. Employees receive ongoing training.

Optum stores its customers' subject identifiable medical information in secure computer systems with strict access controls. Access to the data is permitted only as needed to perform company responsibilities. Data from the automated database can only be accessed through a secure protocol involving personal logon information to establish the identity of the person accessing the data. Only staff approved for access are provided logon access, and data access activity is monitored.

Optum also employs functional and technical security processes to maintain the confidentiality of customer data. All data accessed by approved staff are identified with an ID number that is not directly translatable into a medical record number or social security number. A key to the ID number is maintained at Optum that allows the identification of a specific person from the ID number. This key is kept separate from the database and only accessed when needed to identify a member's records. Additionally, data containing protected health information (PHI) can only be extracted from the

automated database after IRB or Privacy board approval has been received. After it is extracted, all PHI will be housed in a password protected electronic folder.

6.4 Personally Identifiable Information (PII)

Personally identifiable information (PII) and protected health information (PHI) will not be transmitted to GSK according to GSK policy.

6.5 Adverse Event (AE) Reporting

There are no pharmaceutical products or other treatments administered as part of this study. The informed consent form advises subjects to contact their physician directly if they experience any illness, health problems or concerns, but some subjects may instead spontaneously report a medical event in the margin of the written survey or via an unsolicited telephone conversation with Optum or the survey vendor.

If Optum or a vendor working on behalf of Optum receives an adverse event for a GSK product, the adverse event will be reported to GSK pharmacovigilance within one working day. The minimum criteria for reporting an adverse event include an identifiable subject, reporter, medicinal product, and event.

Should a serious adverse event not involving a GSK product occur and become known to Optum, Optum or a vendor working on behalf of Optum will complete a MedWatch form and send the form to the Food and Drug Administration (FDA) Safety Information and Adverse Event Reporting Program within one working day and to GSK pharmacovigilance. The FDA is then responsible for any further reporting obligations in accordance with applicable law.

A serious adverse event (SAE) is defined as any untoward medical occurrence that at any dose:

- Results in death.
- Is life-threatening—the term “life threatening” refers to an event in which the subject was at risk of death at the time of the event; it does not refer to an event that hypothetically might have caused death if it were more severe.
- Requires inpatient hospitalization or prolongation of existing hospitalization.
- Results in persistent or significant disability/incapacity.
- Leads to a congenital anomaly/birth defect.
- Is any other important medical event that satisfies may require intervention to prevent the items listed above.

It is recommended that as much information as possible be collected at the time of the SAE report submission; however, the minimum required data elements for an SAE case to be valid are an identifiable reporter, an identifiable patient, an adverse reaction, and a suspect product.

6.6 Data Storage/Archival

6.6.1 Record Retention

To enable evaluations and/or audits from publishers or GSK, Optum agrees to keep records, including the identity of all participants (sufficient information to link claims data and survey data) and electronic and paper copy data. Optum will store study records in a secure location for a period of six years.

7.2 External Expert/Health Care Professionals (Consultants & Research PIs)

Not applicable.

8 APPENDIX 1. SCHEMATIC OF CLAIMS-LINKED CROSS-SECTIONAL SURVEY STUDY

Patient Identification

Optum identifies potential patient sampling frame in Optum Research Database (ORD) using study inclusion/exclusion criteria

Sample of 2,700 patients meeting study criteria selected for study participation (half of sample in each treatment cohort)

Survey Data Collection (8 weeks per wave)

Week 0

Initial study packets containing an invitation letter on health plan letterhead, consent form, survey, and BRE mailed to identified patients (n= 2,700)

Week 2

Reminder/thank-you postcard mailed to all patients

Week 4

Second study packet mailed to all non-responders

Weeks 1-8

Patients return completed surveys | response rate ~30-35%
n= 385 per cohort

Weeks ~2-9

Thank you letter and post-paid payment mailed to respondents

Analysis

Optum extracts 12 months of respondent's baseline medical and pharmacy claims data from ORD and creates combined analytic file of claims-linked survey data

9 APPENDIX 2. GSK HARMONIZED DEFINITION OF COPD EXACERBATION

The current GSK harmonized definition of COPD exacerbations is provided below. The final definition may be modified at the time of analysis if a more recent harmonized definition is available. The final definition will be provided in the SAP. Exacerbation events and episodes will be identified in the claims period for the 12-month claims observation period (baseline) following the claims lag.

1. EXACERBATION EVENTS

1A. SEVERE EXACERBATION EVENTS

Severe Exacerbation (Hospitalization) Events. COPD-related hospitalization is defined as a severe exacerbation event. Unique hospital admissions and COPD-related hospitalizations are defined with the ICD-10-CM diagnosis codes used to identify COPD-related hospitalizations. Codes will be provided in the SAP.

- If the patient had a qualifying COPD ED event that led to a COPD-related hospitalization, this will count only as a COPD-related hospitalization.
- Hospitalization “via” ED visit or ED visit “leading” to COPD-related hospitalization is defined as an inpatient event that occurred on the same service date or (service date + 1 day) as an ED visit. Allowing for (service date + 1 day) accounts for ED visits that bridge midnight.
- **NOTE:** A qualifying COPD ED event which leads to a non-qualifying hospitalization (i.e. the patient is hospitalized, but the hospitalization does not qualify as COPD-related) is counted as a COPD-related ED event only. The hospitalization in that case is not counted as COPD-related and does not contribute to the episode length.

1B. MODERATE/SEVERE EXACERBATION EVENTS

Moderate/Severe Exacerbation Events are identified by the presence of **emergency department (ED) and/or ambulatory events.**

ED Events: An ED visit with the presence of an ICD-10 code identifying COPD exacerbations **AND** a dispensing of antibiotics or systemic corticosteroids +/- 5 days from the date of the ED visit was considered a moderate/severe exacerbation event.

- Systemic corticosteroids included both oral formulations filled in pharmacies as well as injectable medications administered by a physician.
- A maximum of one ED event per day is counted.
- A COPD-related qualifying ED event leading to a COPD-related hospitalization (occurring on or between the admission and discharge dates of a hospitalization) is included *only* as a COPD-related hospitalization (the ED event was not considered a separate event).
- In claims data, systemic corticosteroids/antibiotic evidence includes prescriptions filled.
- ED visits with qualifying COPD diagnosis codes but NO systemic corticosteroids/antibiotic prescriptions were not included as COPD exacerbations and did *not* contribute to the episode logic.
- Every ED visit meeting the qualification for proximity to systemic corticosteroids/antibiotic prescription/fill was counted as an event (in other words, a single prescription/fill can serve as the qualifying prescription for multiple ED events on different dates).

Ambulatory Events: An office visit or urgent care visit or outpatient hospital visit with the presence of an ICD-10 code for COPD **AND** a dispensing of antibiotics or systemic corticosteroids +/- 5 days from the date of the visit is considered a moderate/severe exacerbation event.

- Every Ambulatory visit meeting the qualification for proximity to an antibiotics or systemic corticosteroid prescription/fill is counted as an event (in other words, a single prescription/fill can serve as the qualifying prescription for multiple Ambulatory events on different dates).

- Surgery-related antibiotics excluded: For both the ED and Ambulatory events, antibiotic prescriptions within 1 week before/after surgical procedures were excluded. Thus, these antibiotic fills were not used to qualify an ED or ambulatory visit as a COPD exacerbation.

2. EXACERBATION EPISODE LOGIC

2A. BASE CASE: SINGLE EVENT EPISODE

In the base case, a COPD exacerbation begins with the earliest occurrence of one of these three events (qualifying COPD hospitalization event, COPD ED Event, COPD Ambulatory Event). In the single event episode, the exacerbation ends 14 days from start (or hospital discharge), whichever is later.

Episode Start date = service date of a qualifying event (IP, ED, outpatient).

- If the qualifying event is a COPD hospitalization, the start date is the admission date.
- The start date is set as the service date of the medical visit, even if an ATB or OCS prescription occurred prior to this visit date.

Episode End Date = Start date + 14 days (if qualifying event is ED or Ambulatory event)

- = Discharge date + 14 days (if qualifying event is an inpatient event)
- If the Episode End Date is on or after the sample ID date (end of claims observation period), then an additional flag is set, **CENSORED=1**

2B. COMPLEX CASE: MULTIPLE EVENT EPISODE

If another qualifying event occurs before the episode End Date, then the episode is extended. The date of the second event is used to reset the End Date per the definition above, using information from this second event. The process continues until a 14-day period with no evidence of exacerbation (qualifying event) occurs. The End Date is set (as defined above).

Episode Length: (End date – Start date) + 1

Episode Severity: If an exacerbation episode includes a qualifying COPD inpatient event, the episode severity is set to Severe. Otherwise, set to moderate/severe.

[figure not shown]
Episode Identification Strategy:

1. Identify all qualifying exacerbation events (Inpatient, ED, Ambulatory)
2. Search for the first exacerbation qualifying event
3. Set START DATE based on the first event using definition above
4. Set a provisional episode END DATE based on definitions above
5. If there is another exacerbation qualifying event between the Start Date and provisional End Date, reset the provisional END DATE based on the definition above
6. Repeat until provisional END DATE has no other qualifying events within 14 days
7. Set episode END DATE as defined above

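### Appendix 2 resets an exacerbation's end date from the later event alone, so an ambulatory visit during a COPD hospital stay can shorten the episode and sometimes split it in two

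*Combined protocol and SAP*

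**What the plan says.** The episode logic is in Appendix 2 (Section 9).

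- **End date, ED or ambulatory event (2A):** "Episode End Date = Start date + 14 days (if qualifying event is ED or Ambulatory event").
- **End date, inpatient event (2A):** "Discharge date + 14 days (if qualifying event is an inpatient event").
- **Several events (2B):** the rule opens with "If another qualifying event occurs before the episode End Date, then the episode is extended" and continues "The date of the second event is used to reset the End Date per the definition above, using information from this second event". Step 5 of the identification strategy gives the same instruction. Neither compares the new end date with the one already set.
- **ED visits during a stay (1B):** a qualifying ED event that leads to a COPD-related hospitalisation, described as "occurring on or between the admission and discharge dates of a hospitalization", counts only as the hospitalisation.
- **Ambulatory visits (1B):** each office, urgent care or outpatient hospital visit with a COPD code and an antibiotic or systemic steroid dispensing within 5 days either side is an event. Visits dated within a hospital stay are not excluded.

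The exacerbation count is used for GOLD A–D (Section 3.4.2 and Appendix 3) and is one of the 21 covariates listed for the inverse probability weighting (Appendix 4). Section 3.3.2.2 attributes exacerbation costs by the same definition.

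**The concern.** A rule meant to extend an episode can shorten it. The reset is harmless when the second event implies a later end date, as it does for a visit after discharge. It fails when the first event is a hospital stay and the second is an ambulatory visit before discharge, because the visit's end date is then the earlier of the two. The text prevents this for ED visits but not for ambulatory visits.

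The affected episodes are those containing a COPD hospitalisation, which the plan grades as severe. A shortened episode has the wrong length and may lose costs dated after the early end. If another qualifying event follows at the right interval, one exacerbation is counted as two. Because 2B both promises an extension and prescribes a reset, two programmers could follow different sentences and produce different counts.

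**Working it through.** The plan gives no figure to reproduce, so the check applies its rules to dated events. Stay lengths and visit dates are illustrative.

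**General case.** Let admission be day 0, discharge day L and the ambulatory visit day v, with 0 < v < L.

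- End date from the stay: L + 14.
- End date after the reset: v + 14.
- Shortening: (L + 14) − (v + 14) = L − v days.

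**Split window.** A later qualifying event on day f opens a second episode under the reset, but not under a later-of rule, in these cases:

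- f from v + 14 to L + 13, if the event must fall strictly before the end date (2B);
- f from v + 15 to L + 14, if the end date itself is included (a possible reading of step 5).

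Either window is L − v days wide.

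**Dated example.** Stay 1–12 March, so L = 11. A qualifying visit on 2 March gives v = 1.

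- Stay: 12 March + 14 = 26 March.
- Reset: 2 March + 14 = 16 March.
- Shortening: 11 − 1 = 10 days.
- Split window: 16–25 March (strict) or 17–26 March (inclusive).
- A qualifying visit on 20 March lies in both. The reset gives two episodes, 1–16 March and 20 March–3 April. The later-of rule gives one, 1 March–3 April.

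**Further cases (days from admission, strict boundary).**

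| Events | Literal reset | Later-of rule |
|---|---|---|
| Stay 0–5 | one, 0–19 | one, 0–19 |
| Stay 0–5, ambulatory day 2 | one, 0–16 | one, 0–19 |
| Stay 0–5, ambulatory days 2 and 17 | two, 0–16 and 17–31 | one, 0–31 |
| Stay 0–5, ED day 2, ambulatory day 17 | one, 0–31 | one, 0–31 |
| Stay 0–5, ambulatory day 8 | one, 0–22 | one, 0–22 |
| Stay 0–20, ambulatory days 1 and 18 | two, 0–15 and 18–32 | one, 0–34 |

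In the last row the reset closes the first episode while the patient is still in hospital.

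**Boundary cases.** A visit on the discharge day or later never shortens the episode. A visit on the admission day shortens it only if the stay is processed before the visit, and the text gives no same-day order.

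**Step 6.** This step closes the episode when no other event falls within 14 days, without saying from which date the 14 days run. Read as a further look-ahead from the provisional end date, it leaves the shortening from the mid-stay visit unchanged but moves the split window 14 days later. For L = 5 and v = 2, the window moves from days 16–18 to days 30–32. In the March example, 16–25 March becomes 30 March–8 April, so the 20 March visit would stay in the same episode.

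**The case against.** The strongest reply is that 2B states its direction: the episode is extended. Its closing rule asks for 14 days without a qualifying event, which sits badly with an end date counted from a day when the patient was still in hospital. Appendix 2 also says that the final definition will be given in the SAP and may change, and a figure in this section is not shown and may illustrate the intended rule. This establishes the likely intent. It does not change the operative instruction in 2B and step 5, which uses the second event only, and deferral to the SAP does not by itself correct the text.

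Several stronger readings are tempting but unsupported.

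- **Any visit during a stay causes the problem.** It does not: ED visits on or between admission and discharge are absorbed.
- **2A contradicts itself.** The prose says that "the exacerbation ends 14 days from start (or hospital discharge), whichever is later". Its natural meaning is 14 days from the later of start and discharge, which agrees with the discharge formula printed below it.
- **The ED linkage rules produce extra exacerbations.** Rule 1A links an "inpatient event that occurred on the same service date or (service date + 1 day) as an ED visit", while 1B refers to the admission-to-discharge range, so an ED visit the day before admission is handled unclearly. Even as a separate event, its 14-day window contains the admission, so there is normally still one severe episode, starting a day earlier. This is a wording point and gives no reason to move the episode start date.
- **The sensitivity analysis by exacerbation history is affected.** It compares patients with and without any exacerbation, and splitting one episode into two cannot change that status.
- **Counts are inflated for hospitalised patients in general.** A split needs a qualifying mid-stay ambulatory event and a later qualifying event within a window of L − v days. How often this happens is not stated.

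**Conclusion.** The defect is real but narrow. On the literal text of 2B and step 5, a qualifying ambulatory event after admission and before discharge of a COPD stay shortens the episode by L − v days: 10 days in the March example and 3 days for a visit on day 2 of a 5-day stay. The shortening does not depend on how step 6 is read or on same-day ordering. The extra episode does depend on step 6, which sets when the later event must fall.

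The conclusion assumes that the count used downstream is of episodes, as 2A suggests when it defines where an exacerbation begins and ends. On that basis it can affect the count behind GOLD A–D, one of 21 weighting covariates, episode length and exacerbation-attributed costs. Whether any GOLD category would change cannot be checked because the classification figure is not shown. The overall effect cannot be sized, and nothing in the documents shows that it would differ between the treatment cohorts or materially move the primary comparison.

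**What to change.** In rule 2B and step 5, replace the reset with: *End Date = the later of the current provisional End Date and the End Date implied by the new event.* Extend the 1B absorption rule so that ambulatory events dated on or between admission and discharge of a COPD-related hospitalisation count only as part of that hospitalisation. The second change also removes the dependence on processing order for an admission-day visit.

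As minor wording, state the date from which step 6's 14 days run, and use the same ED-to-hospital linkage wording in 1A and 1B.

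The cost is a few sentences in Appendix 2 or the SAP and a few lines of code before the claims are extracted for analysis. The one drawback is a small departure from the letter of the sponsor's harmonised definition, which the SAP should record.
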